15.7 Guidelines for Reporting Serious Adverse Events to BTTC

All patients receiving agents will be evaluated for safety. Local IRB SAE reporting procedures are to be followed by all Institutions. At the same time all SAEs must also be reported to the Lead Principal Investigator and the BTTC Coordinating Center.

BTTC SAE reporting requirements and time frames for reporting to the BTTC Coordinating Center are described below:

Adverse Event Reporting for Investigator-Initiated Clinical Trials			
UNEXPECTED EVENT		EXPECTED EVENT	
Grade 2 & 3	Grades 4 and 5	Grades 1-3	Grades 4 and 5
Attribution of Possible, Probable or Definite	Regardless of Attribution		Regardless of Attribution

Expedited report to MDACC OMCR within 5 working days.
	
Report by phone to MDACC OMCR Within 24 hrs. Expedited report to follow within 5 Working days.
	
Adverse Event Expedited Reporting is NOT required.
	
Expedited report, including Grade 5 Aplasia in leukemia patients, within 5 Working days.

Grade 1 – Adverse Event Expedited Reporting not required.
	
This includes deaths within 30 days of the last dose of treatment with an investigational agent regardless of attribution. Any late death attributed to the agent (possible, probable, or definite) should be reported within 5 working days.
		
This includes deaths within 30 days of the last dose of treatment with an investigational agent regardless of attribution. Any late death attributed to the agent (possible, probable, or definite) should be reported within 5 working days. Grade 4 Myelosuppression or other Grade 4 events that do not require expedited reporting will be specified in the protocol.

For Hospitalization Only – Any medical event equivalent to CTC Grade 3, 4, 5 which precipitated hospitalization (or prolongation of existing hospitalization) must be reported regardless of requirements for phase of study, expected or unexpected and attribution.
			

Expedited reporting may not be appropriate for specific expected AEs for certain later Phase II and Phase III protocols. In those situations the AE that will not have expedited reporting must be specified in the text of the approved protocol.
			

The BTTC Coordinating Center will maintain documentation of all Serious Adverse Events from each institution. The BTTC Coordinating Center will notify all investigators of any serious and unexpected adverse experiences that are possibly related to the study agent/s. The investigators are to file a copy with their protocol file and send a copy to their IRB according to their local IRB’s policies and procedures.

All serious adverse events that are unexpected and assessed to be possibly related to the study agents must be reported to the FDA by the lead investigator (or their designee) as a 15-day post-marketing ‘Alert Report’. An unexpected adverse event is one that is not already described in the study agent Investigator Brochure(s). The lead principal investigator (or their designee) also has the obligation to report serious adverse events to their IRB, and UCB. This includes serious, related, labeled (expected) and serious, related, unlabeled (unexpected) adverse experiences.

The BTTC Coordinating Center will forward all SAE reports to the lead IRB via the lead investigator, FDA (when applicable), and UCB within 2 business days after sending to the lead PI.

UCB, S.A.	FDA Med Watch 15-day Alert Report
[contact] [contact] x Option 4 E-mail: [contact]	Phone: [name] Fax: [name] or by mail to MedWatch Center for Biologics Evaluation and Research Food and Drug Administration [name] FAX: [name] or by mail to MedWatch, Food and Drug Administration, [name]

SAEs should be recorded on a Multicenter SAE Form (Appendix 17.8). Multicenter SAE forms are to be submitted via EDMS or faxed to:

MDACC Office of Multicenter Clinical Research
Attn: BTTC Project
[contact]
EDMS: <https://iview.mdanderson.org/>
[contact]

Follow-up information:

Additional information may be added to a previously submitted report by any of the following methods:

- Adding to the original Multicenter SAE SAE report and submitting it as follow-up
- Adding supplemental summary information and submitting it as follow-up with the original Multicenter SAE form.
- Summarizing new information and faxing it with a cover letter including subject identifiers (i.e. D.O.B. initial, subject number), protocol description and number, if assigned, suspect drug, brief adverse event description, and notation that additional or follow-up information is being submitted (The subject identifiers are important so that the new information is added to the correct initial report)

Occasionally BTTC may contact the reporter for additional information, clarification, or current status of the subject for whom an adverse event was reported.

Assessing Causality:

Investigators are required to assess whether there is a reasonable possibility that the study agent/s caused or contributed to an adverse event. The following general guidance may be used.

Yes: If the temporal relationship of the clinical event to the study agent/s administration makes a causal relationship possible, and other drugs, therapeutic interventions or underlying conditions do not provide a sufficient explanation for the observed event.

No: If the temporal relationship of the clinical event to the study agent/s administration makes a causal relationship unlikely, or other drugs, therapeutic interventions or underlying conditions provide a sufficient explanation for the observed event.

15.8 Guidelines & Procedures for reporting Violations, Deviations and Unanticipated Problems

Neither the FDA nor the ICH GCP guidelines define the terms “protocol violation” or “protocol deviation.” The definition is often left to the Lead Institution IRB. Accordingly, since MDACC is the Coordinating Center and the Protocol Chair must adhere to those policies set by the MDACC IRB, the definitions for protocol violation and deviation as described by the MDACC IRB will be applied for reporting purposes for all institutions participating in the MDACC Multi-center Project. Definitions, reporting guidelines and procedures for reporting violations, deviations and/or unanticipated problems are described in the BTTC Operations Manual.

Protocol violations/deviations/unanticipated problems occurring at a participating institution will be submitted to that institution’s own IRB. A copy of the participating institution’s IRB violation/deviation/unanticipated problem report will be forwarded to the BTTC Coordinating Center by mail, facsimile, or via email (password protected document) within 7 calendar days after the original submission.

MDACC Office of Multicenter Clinical Research
Attn: BTTC Project
[contact]
Email: [contact]

BTTC Coordinating Center: Upon receipt of the violation/deviation/unanticipated problem report from the participating institution, the BTTC Coordinating Center will submit the report to the lead Protocol Chair for review. Subsequently, the participating institution’s IRB violation/deviation/unanticipated problem report will be submitted to the MD Anderson Cancer Center IRB for review.

15.9 Institutional Review

Each cooperating center will submit the protocol to its own IRB. Documentation of the IRB approval will be forwarded to the MDACC OMCR at UT MDACC before a patient from that institution can be registered on protocol. No changes in the protocol will be allowed unless approved by the principal investigator and BTTC.

15.10 Protocol Revisions and Closure

Non life-threatening revisions: BTTC investigators will receive written notification of protocol revisions regarding non life-threatening events.

Life-threatening revisions: BTTC investigators will receive telephone notification of life-threatening revisions with follow-up by fax and/or e-mail. Life-threatening protocol revisions will be implemented immediately.

Protocol closures and temporary holds: BTTC investigators will receive email notification of protocol closures and holds. Closures and holds will be effective immediately. Centers will be updated on an ongoing basis about protocol accrual data so that they will be aware of imminent protocol closures.

15.11 Quality Assurance

The BTTC Quality Assurance procedures and reports are described in detail in the BTTC Operations Manual. However, an abbreviated description is provided below.

BTTC Quality assurance measures are provided by three mechanisms: ongoing in-house monitoring of protocol compliance, on-site audits, and response reviews. All data submitted to the MD Anderson OMCR at UT MD Anderson will be monitored in-house for timeliness of submission, completeness, and adherence to protocol requirements. Data monitoring will begin at the time of patient registration and will continue during protocol performance and completion. The MD Anderson Protocol Manager will perform the ongoing protocol compliance monitoring with the support of the BTTC study investigators.

In the absence of a sponsor monitoring requirement, or agency, institutions participating in BTTC Protocols may be subject to on-site auditing conducted by the MD Anderson OMCR as described in the MD Anderson OMCR's Multi-Center Audit Plan for the BTTC consortium. The Multi-Center Audit Plan does not replace the in-house monitoring described in this manual. On-Site auditing combined with the in-house monitoring are intended to enhance the reliability and validity of clinical trial data from BTTC institutions through the use of routine monitoring & auditing procedures.

15.12. Guidelines and Procedure for Unblinding Treatment

The site/treating Principal Investigator may request unblind the patient's treatment under certain circumstances:

- (1) A life –threatening event;
- (2) protocol-defined seizure activity;
- (3) An AE that is concerning to the site Primary Investigator
- (4) At the time study treatment is discontinued.

The unblinding procedure is outlined below. All parties must strictly adhere to the procedure in order to maintain protocol integrity.

1. The treating physician will call and email [name] and/or his back up to request the unblinding.
2. The treating physician completes the Unblinding Request form:
3. The treating physician will sign and date the completed request form.
4. The treating physician will scan and e-mail the completed unblinding request form to [name] or designee and cc MDA Anderson OMCR BTTC Staff ([contact])
5. If [name], or his back-up, approves the unblinding, he will sign, date, scan, and email the Unblinding Request form to the study statistician, [name], [name] back-up, and cc the M.D. Anderson OMCR and the requesting physician.
6. [name], and/or his back-up, will unblind the patient, and email **the treatment assignment to the treating physician only**. [name] will follow up by sending the completed patient unblinding notification memo to the requesting physician.
7. The treating physician will document the unblinding request and outcome in the patient's chart following their institution's policy and procedures **within 24 hours of the unblinding.**
8. The OMCR will notify the MDA IRB and the MD Anderson DSMB of routine patient unblindings at the time of the annual protocol approval. The OMCR will notify the DSMB of each emergency unblinding as they occur.
9. All research staff involved in the activity for this protocol should continue to remain blinded to drug assignment/randomization.
10. If the unblinded patient experienced an SAE, the SAE is to be processed per the protocol, BTTC Operation's Manual, and the institution's policy and procedure. Patient will be taken off treatment and followed for 30 days after last dose or until the event has been resolved.

Contact Information:

NAME	PHONE NUMBER	EMAIL ADDRESS
- [name]. (study chair)	[contact]	[contact]
[name], M/D. ([name] back-up)		
[name]. (study biostatistician)	[contact]	[contact]
[name] (1st back up to [name])	[contact]	[contact]
[name] (2nd back up for [name])	[contact]	[contact]

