9.0 CRITERIA FOR EVALUATION AND ENDPOINT DEFINITIONS

9.1 Definition of Seizure

Patients and caregivers will be educated about signs and symptoms of seizures using a standard education sheet (Appendix 17.5). They will be instructed to contact the investigator immediately for possible seizure activity. For study purposes, confirmed seizures will include any of the following:

1. Simple partial seizures:
 - a) with motor symptoms: focal motor movements, versive/postural movements
 - b) with sensory symptoms: olfactory sensations
 - c) with autonomic signs
 - d) with psychic symptoms (sudden reversible loss of expressive/receptive speech)
2. Complex partial seizures
 - a) with impairment of consciousness only
 - b) with impairment of consciousness plus automatisms (lip smacking, fumbling, etc)
3. Partial seizures with secondarily generalized seizures
 - a) Unconsciousness with myoclonic jerks with or without tongue-bite or stiffening
 - b) Unconsciousness with tonic spasm, without myoclonic jerks, with or without tongue-bite
 - c) Unconsciousness with tongue-bite without myoclonic jerks or stiffening
 - d) Unconsciousness or staring with one of the following preceding symptoms perceived by the patient:
 - A rising feeling from the abdomen to the throat
 - Smelling of odd scents
 - Stiffening or convulsions in the face or limb(s)
 - Turning the head to one side

Excluded attacks are those deemed by the treating physician to be non-neurologic in origin and are comprised of:

- Merely staring
- Exclusively unconscious with or without incontinence for urine
- Solely disturbances of seeing, feeling, or thinking

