9.2 Clinical Event Committee

Medical records from the first post-event physician visit and other relevant medical record information will be forwarded to a blinded “clinical event committee” (CEC) that will review source documents and classify events as seizures or otherwise. The study investigators and the CEC will be instructed to utilize a standard seizure definition (Section 9.1). The committee will be composed of board-certified neurologists who have no other involvement with the study. Each event will be adjudicated by 2 independent reviewers. If the reviewers do not agree about the nature of the event, a third

independent reviewer will adjudicate the event. Additional details regarding the clinical event committee are presented in the Clinical Event Committee Charter.

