10.0 CRITERIA FOR REMOVAL FROM TREATMENT

10.1 Criteria for Removal from Protocol Treatment:

- a. Completion of one year of therapy.
- b. Unacceptable toxicity (**see Section 6.1.3**).
- c. Seizure (as defined in Section 9.1).
- d. The patient may voluntarily withdraw from treatment at any time for any reason.
- e. Medical or psychiatric illness which in the investigator's judgment renders the patient incapable of further therapy.
- f. Pregnancy.

All reasons for discontinuation of treatment must be documented in the flow sheets.

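### Section 15.12 does not require the event record before non-emergency unblinding, so the treating physician may know the arm when writing up, or first judging, an endpoint event

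*Combined protocol and SAP*

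**What the plan says.** **Grounds for unblinding.** Section 15.12 lists four. Two matter here: "2) protocol-defined seizure activity" and "4) At the time study treatment is discontinued". A first seizure on drug meets both, because section 10.1 lists "c. Seizure (as defined in Section 9.1" as a reason to stop treatment.

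**Procedure.** The physician calls and emails, then completes and signs a request form. A designated approver must agree. Step 6 sends the "treatment assignment to the treating physician only". Step 7 requires the physician to "document the unblinding request and outcome in the patient's chart" within 24 hours of the unblinding. Step 9 says research staff stay blinded. No step refers to the event record or to adjudication.

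**Reporting and site call.** On possible seizures, section 9.1 says of patients and caregivers: "They will be instructed to contact the investigator immediately for possible seizure activity". It also gives the site physician a say in what does not count: "Excluded attacks are those deemed by the treating physician to be non-neurologic in origin".

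**Adjudication.** Section 9.2: "Medical records from the first post-event physician visit and other relevant medical record information will be forwarded to a blinded" committee. Its members are neurologists with no other role in the trial. Two review each event, with a third if they disagree. Further detail is left to a charter that is not among the documents. The only redaction stated for patient reports sent to the coordinating office (section 15.4) is of name and social security number.

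**The concern.** The primary endpoint is time to first seizure. Section 8.5 makes EEG optional because the diagnosis usually rests on history, so the physician's narrative carries much of the endpoint. There are two routes by which knowledge of the arm could reach it.

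- **Packet route.** After a first seizure the physician can be unblinded and then write the post-event record from which the committee works. The note of the unblinding sits in the same chart.
- **Early-stop route.** A patient unblinded under another ground without a seizure may later have an attack. A physician who may know the arm then makes the first call, including the non-neurologic exclusion.

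Arm-aware reporting could produce a false claim of benefit or hide a true one. With about 42 events expected, a few differently judged events can matter.

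**Working it through.** **1. Order of events.** A patient phones at once (9.1). The unblinding request also goes by phone and email (15.12, step 1). The chart entry follows within 24 hours of unblinding (step 7). The committee's core material comes from the first post-event visit (9.2), for which no deadline is given. Off-treatment data and source documents are due within 10 days of the last dose (15.5). These timings allow the assignment to be known, and possibly charted, before the write-up. Nothing requires the reverse order.

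**2. The plan's own figures (11.1).** HR = ln(0.92)/ln(0.80) = 0.374, as stated. Log-rank simulation with 298 patients, one-year censoring and 15% loss gives 83.6% power, as stated. Expected events without loss: 151 × (0.20 + 0.08) = 42.3, against 42 stated. The concern changes none of these.

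**3. Set-up for illustration.** 151 per arm, exponential times, 20% v 8% risk, 15% yearly loss, unstratified Cox likelihood-ratio test at two-sided 0.05, single look. Base: 11.1 v 28.0 events, power 85%. Type I error uses 20% risk in both arms unless stated. Every difference between arms below is assumed; the documents give none.

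**4. Packet route.** Reference: 10% of events rejected in each arm. Average shift = share of events unblinded first × shift among those; for example 0.5 × 10 points = 5 points. A rejected patient stays at risk.

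| Average shift (points) | Type I error if lacosamide events are rejected more | Same, 14% risk in both arms | Power if placebo events are rejected more |
|---|---|---|---|
| 0 | 5.0% | 5.0% | 80% |
| 5 | 5.6% | 5.6% | 74% |
| 10 | 7.1% | 6.6% | 67% |
| 20 | 14% | 10.8% | 50% |

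A separate log-rank run (12,000 trials per case) gave type I error of 4.8, 5.2, 6.9 and 13.8% and power of 80, 74, 66 and 49%. The 20-point row means rejecting 30% v 10% of first events: 28 × 0.30 = 8.4 v 28 × 0.10 = 2.8.

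**5. Early-stop route.** Section 2.5 gives discontinuation for adverse events of 17% at 400 mg/day, 8% at 200 mg/day and 5% on placebo, from add-on epilepsy trials. Section 2.3 gives 23.8% of brain tumor patients on AEDs with side effects that led to a change or stop. Assume stops spread evenly over 18 weeks, the placebo hazard afterwards, and all placebo events called. At 17%, 151 × 0.17 = 25.7 patients stop, with on average 1 − 9/52 = 0.83 year left. That gives 25.7 × (1 − e^(−0.223 × 0.83)) ≈ 4.3 events before allowing for loss and earlier seizures. The simulation gives 3.9 (of 13.5 lacosamide events), against 1.1 of 28 on placebo.

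| Lacosamide stops | Lacosamide events after a stop | Type I error, half called | None called |
|---|---|---|---|
| 8% | 1.8 | 5.3% | 6.0% |
| 17% | 3.9 | 5.9% | 9.0% |
| 23.8% | 5.5 | 6.7% | 13% |

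With 14% risk in both arms, the 17% row gives 5.8% and 7.7%. If all events are called, type I error is 5% and power at 17% stops is 69%. That loss of power is lost drug effect, not bias. The table treats every stop as unblinded, so the figures are upper limits.

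**6. Is a late attack captured?** Sections 8.4, 11.1 and 11.2.1 point to seizure follow-up for the full year. Figure 8-1, footnote a, ties the four-weekly calls to time on treatment. If capture ends 30 days after stopping, about 0.45 lacosamide events follow a stop and type I error stays at 5%.

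**The case against.** The strongest reply is that the blind is already protected. Section 9.2 requires a blinded committee of uninvolved neurologists, step 6 limits who receives the assignment, and step 9 keeps research staff blinded. The seizure ground presupposes that the event has been judged against section 9.1, and a signed form and an approval come before release. A first convulsion is also an example of a serious event in section 15.6, which creates a separate report. The charter is the natural place for packet masking, and the request form and memo (appendices 17.6 and 17.7) may set timing.

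Most of this stands. A reader might infer that the committee adjudicates unblinded, or that first seizures are called by unblinded physicians. The documents support neither: blinding is asserted and only the redaction procedure is not described, while the first call on drug is normally blind. The charted outcome may be only the decision on the request, not the arm. The 9.1 exclusion may not keep events from the committee either, since 9.2 has it sort events into seizures and others.

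What remains is the order. Neither the form, the approval nor the safety report is required to follow a finished event record. Masking a packet cannot undo a narrative written with the arm known. And nothing states that attacks the treating physician excludes are forwarded.

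**Conclusion.** The point holds as a cheap procedural improvement. Following section 15.12 as written, a treating physician can write up a first seizure, or judge a later attack, knowing the arm.

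The documents do not show that bias will occur, or in which direction, and a reader should not infer that the result is likely to favour lacosamide. Moderate assumed cases (a 5-point average shift, or half of post-stop lacosamide events called at 17% stops) give type I error of 5.6% and 5.9%. The same 5-point shift in the other direction costs about 6 points of power. Values of 9 to 14% need extreme assumptions: rejection of 30% v 10% of events by independent neurologists, or every stop unblinded with no later lacosamide seizure called and every placebo one called. Neither arm is on study drug by then, so the motive for such one-sided calls is weak.

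The conclusion rests on the charter and the unblinding form and memo not already setting the order. If they do, a cross-reference is enough.

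**What to change.** - **15.12:** for non-emergency requests that follow a possible seizure, release the assignment only after the site has submitted a dated event form, narrative and available source records. This is the main change.
- **9.1 and 9.2:** forward every possible attack, so that the blinded committee rather than the treating physician decides the exclusion.
- **9.2:** state, or cross-reference the charter, that the assignment and any unblinding note are removed from each packet.
- **Data and analysis:** record whether unblinding preceded the event record. As a sensitivity analysis, repeat the primary test counting attacks first recorded after unblinding as seizures. Censoring at unblinding would address only the early-stop route, because a seizure that prompts unblinding is dated before it.

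I would not postpone unblinding for patients who stop drug without a seizure. That is a trade-off, since it withholds the assignment from clinicians choosing later treatment.

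The cost is a short delay to non-emergency unblinding and a check of about 42 or more packets. Emergency unblinding, sample size, alpha and the primary test are unchanged.

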Lacosamide is well-tolerated and has no known drug-drug interactions. In controlled clinical trials, the rate of discontinuation as a result of an adverse event was 8% and 17% in patients randomized to receive lacosamide at the recommended doses of 200 and 400 mg/day, respectively, 29% at 600 mg/day, and 5% in patients randomized to receive placebo. The adverse events most commonly leading to discontinuation were dizziness, ataxia, vomiting, diplopia, nausea, vertigo, and vision blurred. Abnormalities in liver function tests have been observed in controlled trials with lacosamide in adult patients with partial-onset seizures who were taking 1 to 3 concomitant AEDs. Elevations of ALT to $\geq 3 \times$ the upper limit of normal (ULN) occurred in 0.7% (7/935) of lacosamide patients and 0% (0/356) of placebo patients. One case of hepatitis with transaminases $> 20 \times$ ULN was observed in one healthy subject 10 days after lacosamide treatment completion, along

with nephritis (proteinuria and urine casts). Serologic studies were negative for viral hepatitis. Transaminases returned to normal within one month without specific treatment. At the time of this event, bilirubin was normal. The hepatitis/nephritis was interpreted as a delayed hypersensitivity reaction to lacosamide.

A list of possible adverse events is provided in Section 3.12. This includes events reported by patients treated with lacosamide in all clinical trials in patients with partial-onset seizures, including controlled trials and long-term open-label extension trials, as well as events identified during post approval use of lacosamide. Because the latter are reported voluntarily from a population of uncertain size, it is not always possible to reliably estimate their frequency or establish a causal relationship to drug exposure. The most frequently reported adverse events include dizziness, vertigo, diplopia, blurred vision, nystagmus nausea/vomiting, diarrhea, fatigue, headache, somnolence, tremor, ataxia, and imbalance. Post approval adverse events of potential significance include bradycardia and rash.

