11.2.5 Adverse Events

Clinical and laboratory adverse events will be coded using the NCI's Common Terminology Criteria for Adverse Events (CTCAEv4.0). The CTCAEv4.0 will be attached to the clinical database.

Summaries of unique adverse events will include

- all treatment emergent adverse events,
- all treatment emergent adverse events by the worst grade,
- all related treatment emergent adverse events,
- all related treatment emergent adverse events by the worst grade,
- all adverse events leading to study drug discontinuation

Treatment emergent adverse events are

- Events with onset dates on or after the start of treatment and up to 30 days after the permanent discontinuation of the study medication
- Continuing adverse events diagnosed before the start of treatment and getting worse in grade or relationship to treatment after the start of treatment.

Related adverse events include all those classified by the investigator as definitely, probably, or possibly related to the study drugs. Events for which the investigator did not record relationship to study drug will be considered related to study drug.

Multiple events will be counted once only per patient in each summary. In the presentation, Adverse Event Categories will be sorted in alphabetical order. Within Categories adverse events will be sorted in descending order of total events. For summaries by severity, the most severe event will be selected.

Deaths and serious adverse events

Serious adverse events and deaths will be listed. Data from the adverse event page that specify the event is serious will be used to generate the listing.

Summaries of serious unique adverse events will include:

- all serious treatment emergent adverse events,
- all related serious treatment emergent adverse events by the worst grade,

11.3 Patient Reported Outcomes.

The sample size for this trial was based on the primary endpoint of the study.

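### Section 15.12 lets the treating physician learn the arm for a non-emergency adverse event, or when treatment stops, with no visible step fixing grade and relatedness first, so the related-event summaries can rest on unblinded judgements.

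*Combined protocol and SAP*

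**What the plan says.** Section 15.12 gives four reasons for which the site or treating principal investigator may ask to unblind. Reason (1) is a life-threatening event and reason (2) is seizure activity as the protocol defines it. Reason (3) is "An AE that is concerning to the site Primary Investigator", with no threshold of grade or seriousness. Reason (4) is "At the time study treatment is discontinued". Because (1) and (4) are listed separately, (3) reaches events that are not life-threatening in patients still on study drug.

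The release procedure has a call and email, a signed form and an approval. Under step 5, if the approver or his back-up "approves the unblinding, he will sign, date, scan, and email the Unblinding Request form to the study statistician", the process moves on. No approval criteria are given. Step 6 sends "the treatment assignment to the treating physician only". Step 7 asks for the unblinding to be charted within 24 hours afterwards.

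On attribution, 11.2.5 states: "Related adverse events include all those classified by the investigator as definitely, probably, or possibly related to the study drugs". Section 15.7 adds: "Investigators are required to assess whether there is a reasonable possibility that the study agent/s caused or contributed to an adverse event". Neither says that the judgement is made blinded. Section 11.2.5 also tabulates "all adverse events leading to study drug discontinuation".

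**The concern.** Relatedness is a judgement, and in this population it is an open one. Section 3.12 lists headache, nausea, vomiting, fatigue, ataxia and somnolence as lacosamide effects. High-grade glioma and its treatment can produce the same complaints, and 6.1.1 permits standard and experimental anti-tumour therapy. The causality guidance in 15.7 points to a negative answer when other drugs or underlying conditions sufficiently explain the event. A physician who knows that the patient is on placebo has no active study drug to blame. One who knows that the patient is on lacosamide has a listed toxicity to hand.

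If the arm is known when the judgement is entered, the threshold for calling an event related can differ between arms. A comparison of related events then mixes drug effect with knowledge of assignment. Section 9.3 asks whether worsening symptoms offset any seizure benefit, so tolerability matters to how the trial is read. Seizures (9.2) and EEGs (9.4) have blinded review; adverse-event attribution has no counterpart.

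**Working it through.** The plan states no figure on this point, so there is none to reproduce. The check has two parts: the order of events that the text permits, and the scale under stated assumptions.

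**Order of events**

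- Release of the arm: 15.12 steps 1-6. None mentions grade or relatedness.
- Who learns it: the treating physician. The opening of 15.12 identifies the requester as the site or treating principal investigator, so this is probably, though not explicitly, the person who classifies the event.
- When the judgement is due: events are evaluated monthly (8.8) but reported at least quarterly (15.6), and adverse-event data are due up to 14 days after each quarterly visit (15.5). Expedited reports on unexpected grade 2-3 events are due within 5 working days (15.7).
- Example: a headache in month 5 prompts a request under (3). The arm is released. Relatedness is submitted with the data for the month 7 visit. Nothing in the text is breached.

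**Which outputs use the judgement**

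- Of the five main summaries in 11.2.5, two use relatedness: related events, and related events by worst grade.
- Of the two serious-event summaries, one does: related serious events by worst grade.
- In the 15.7 table, attribution decides expedited reporting for unexpected grade 2-3 events. Grade 4-5 events, and events of grade 3 or above that lead to hospitalisation, are reported whatever the attribution.
- Missing relatedness counts as related (11.2.5). That does not correct an entry made with knowledge of the arm.

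**Scale, on assumptions that are not in the documents**

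Let r be the proportion of each arm with a concerning event, f the share of these unblinded before judgement, and s the shift in the probability of a related call (up on lacosamide, down on placebo). The spurious between-arm difference is r × f × 2s. With 151 patients per arm (11.1):

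| r | f | s | Difference | Patients per 151 |
|---|---|---|---|---|
| 0.10 | 0.10 | 0.10 | 0.2 points | 0.3 |
| 0.20 | 0.25 | 0.20 | 2.0 points | 3.0 |
| 0.20 | 0.50 | 0.30 | 6.0 points | 9.1 |

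A second route uses adverse-event discontinuations, all of which could prompt a request under (4). Section 2.5 reports that in earlier trials "the rate of discontinuation as a result of an adverse event was 8% and 17" per cent at 200 and 400 mg/day, and 5% on placebo. At the 400 mg/day rate, 151 × 0.17 = 25.7 and 151 × 0.05 = 7.6 patients.

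Assume that a blinded physician calls half of these related: 8.5% against 2.5%, a difference of 6.0 points. Now assume that a quarter are unblinded first, with all of those called related on lacosamide and none on placebo:

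- lacosamide: 0.17 × (0.5 + 0.5 × 0.25) = 10.6%
- placebo: 0.05 × 0.5 × 0.75 = 1.9%

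The difference is 8.75 points, of which 2.75 are spurious. This lies within the range in the table.

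**The case against.** Much of the case on the other side stands, and it limits the point.

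- **Discontinuations.** A reader might infer that the arm drives who stops study drug. The documents do not support that as a general reading. Reason (4) accompanies a stop. Step 10 takes an unblinded patient with a serious event off treatment in either arm. The discontinuation summary is not filtered by relatedness. Only non-serious events unblinded under (3) in patients still on drug leave the stopping decision open, and nothing in the documents puts a size on that.
- **An extreme split.** A reader might push the second calculation to full unblinding and obtain 17% related on lacosamide against 0% on placebo. That is an assumed bound. It ignores the guidance in 15.7 to answer in the negative when another explanation suffices. The underlying rates also come from patients with long-standing epilepsy who were taking other antiepileptic drugs.
- **Under-reporting of placebo events.** A reader might infer this in general. Only expedited reporting of unexpected grade 2-3 events without hospitalisation is exposed. Those events still go on the adverse event form and into the all-causality tables.
- **Trial conclusions.** Section 11.2.5 specifies summaries and names no test on related events. All-causality summaries do not use relatedness, nor does the primary analysis.
- **Unseen material.** The content of the request form (Appendix 17.6), the serious adverse event form (17.8) and the BTTC Operations Manual is not in the text supplied. Any of them may already capture grade and relatedness.
- **Practice.** Unblinding needs approval, and monthly review may mean that many judgements come first anyway.

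What survives is narrow: the visible text permits the arm to be known before relatedness is recorded, and no analysis separates the two situations.

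**Conclusion.** The point holds as a gap in sequence. Following 15.12 as written, the treating physician can learn the arm for a non-emergency event, or at discontinuation, before grade and relatedness are recorded. The related-event summaries, the related-serious-event summary and one category of expedited report can then rest on unblinded judgement. The text permits that order; it does not require it.

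The size is not derivable, because the frequency of unblinding is not stated. The range of 0.2 to 6 points rests wholly on the assumed r, f and s, and on the treating physician being the one who classifies the event. Not affected are the primary endpoint, the all-causality tables, grade 4-5 reporting under the 15.7 table, and stopping after an unblinded serious event under step 10.

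**What to change.** In 15.12, for non-emergency requests under (3) and (4), require grade and relatedness to be entered and dated on the adverse event form before the arm is released. Have the request form confirm this, if it does not already. For life-threatening events do not delay unblinding; flag the event as assessed after unblinding.

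In 11.2.5, state that related-event summaries use the pre-unblinding assessment, and report by arm the number of events assessed after unblinding. Keep the discontinuation summary on actual discontinuations and flag those decided after unblinding. Using a pre-unblinding decision there would misrecord patients who stopped later.

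The cost is one procedural step, possibly one line on an existing form, and a short addition to 11.2.5, with a short delay to non-emergency requests. Nothing here sets a condition on the decision to continue or stop study drug.
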